7.2.1.2. Treatment Visits during Study

Each subject will subsequently return to the clinical research facility during Week 12 (Visit 3), Week 24 (Visit 4), Week 36 (Visit 5), Week 48 (Visit 6), Week 60 (Visit 7), Week 72 (Visit 8), Week 84 (Visit 9), Week 96 (Visit 10), Week 108 (Visit 11), Week 120 (Visit 12), Week 132 (Visit 13), Week 144 (Visit 14), Week 156 (Visit 15), Week 168 (Visit 16), Week 180 (Visit 17), Week 192 (Visit 18), Week 204 (Visit 19), Week 216 (Visit 20), Week 228 (Visit 21) and Week 240 (Visit 22).

7.2.1.3. End of Treatment

It is planned that each subject will return to the clinical research facility at Week 240 (Visit 22) for the End-of-Treatment Visit. However, this study duration may be altered per the conditions noted in Section 6.2.1. In this case, the timing of the End-of-Treatment Visit, will be adjusted appropriately. If the patient terminates the study early because ataluren is commercially available in that country, then the patient only needs to return for the End-of-Treatment Visit.

If the subject discontinues prematurely, except patients switching to commercial ataluren (ie, before Week 240) and the last visit to the investigator site occurred >3 weeks previously, the procedures that would normally be performed at Week 240 should be performed as a Premature Discontinuation Visit before the subject leaves the study.

7.2.1.4 Post-Treatment Visits

All patients who discontinue at luren must return for a Post-Treatment Visit at the investigator site 6 weeks (±7 days) after the last dose of at luren for final study-related evaluations. If the End-of-Treatment Visit occurs >6 weeks after the last dose of at luren, the Post-Treatment Visit does not need to be performed. For patients discontinuing the study to transition to commercially available at luren, an End-of-Treatment visit should be performed for that patient. However, a 6-Week Post-Treatment Visit is not required for these patients.

7.2.2. Informed Consent

The investigator or sub-investigator must inform each prospective subject of the nature of the study, explain the potential risks, and obtain written informed consent/assent from the subject and/or the parent/legal guardian prior to performing any study-related screening procedures. Subjects will be re-consented with the appropriate age-related documents as needed, if required by local regulations.

7.2.3. Clinical/Medication History

The investigator should review the study candidate's clinical history, including details relating to DBMD and any other medical conditions. Information regarding current medications must be recorded in the source documents and on the concomitant medication CRF.

7.2.4. Hepatitis Screen

Tests include hepatitis A antibody, hepatitis B core antibody, and hepatitis C antibody. The Central Laboratory Manual should be consulted for collection, processing, and shipping details. *Note: Only hepatitis B and C results are required for eligibility determination.*

7.2.5. Vital Signs

Vital signs (including systolic and diastolic blood pressure, pulse rate, and body temperature) will be monitored at Screening (Visit 1), Week 1 (Visit 2), Week 12 (Visit 3), Week 24 (Visit 4), Week 36 (Visit 5), Week 48 (Visit 6), Week 60 (Visit 7), Week 72 (Visit 8), Week 84 (Visit 9), Week 96 (Visit 10), Week 108 (Visit 11), Week 120 (Visit 12), Week 132 (Visit 13), Week 144 (Visit 14), Week 156 (Visit 15), Week 168 (Visit 16), Week 180 (Visit 17), Week 192 (Visit 18), Week 204 (Visit 19), Week 216 (Visit 20), Week 228 (Visit 21) and Week 240 (Visit 22 End-of-Treatment/Premature Discontinuation) and at the Post-Treatment Visit (6 weeks post discontinuation of ataluren). The pulse rate and blood pressure determinations will be performed with the subject in a sitting position after a 5-minute rest.

7.2.6. Brooke Upper Extremity Functional Rating Scale

Upper extremity function will be assessed in all patients who are nonambulatory at study entry using the Brooke Upper Extremity Functional Rating Scale [Brooke 1981, Lue 2006, Florence 1984]; this evaluation will be performed at Screening (Visit 1). The Study Manual provides additional information regarding the performance of this procedure.

7.2.7. Height/Ulna Length/Arm Span

Height (in cm) will be measured at Screening (Visit 1), at Week 24 (Visit 4), Week 48 (Visit 6), and Week 72 (Visit 8), Week 96 (Visit 10), Week 120 (Visit 12), Week 144, Week 168 (Visit 16), Week 192 (Visit 18), Week 216 (Visit 20) and Week 240 (Visit 22 End-of-Treatment/Premature Discontinuation) in ambulatory patients.

For nonambulatory patients, due to the difficulty in obtaining an accurate standing height measurement, ulna length and arm span will be used, as a surrogate measure for height (see Study Manual). Ulna length and arm span (in cm) will be measured at Screening (Visit 1), Week

24 (Visit 4), Week 48 (Visit 6), and Week 72 (Visit 8), Week 96 (Visit 10), Week 120 (Visit 12), Week 144, Week 168 (Visit 16), Week 192 (Visit 18), Week 216 (Visit 20) and Week 240 (Visit 22 End-of-Treatment/Premature Discontinuation).

7.2.8. Physical Examination

A full physical examination (including evaluation of cardiovascular system, chest and lungs, thyroid, abdomen, nervous system, skin and mucosae, musculoskeletal system, eyes, ears, nose, mouth, throat, spine, lymph nodes, extremities, and genitourinary) will be conducted at Screening (Visit 1), at Week 48 (Visit 6), Week 96 (Visit 10), Week 144 (Visti 14), Week 192 (Visit 18), and Week 240 (Visit 22 End-of-Treatment/Premature Discontinuation).

Physical exams may also be performed at any time during the study as clinically indicated.

7.2.9. Weight

Weight (in kg) will be measured at Screening (Visit 1), Week 1 (Visit 2), Week 12 (Visit 3), Week 24 (Visit 4), Week 36 (Visit 5), Week 48 (Visit 6), Week 60 (Visit 7), Week 72 (Visit 8), Week 84 (Visit 9), Week 96 (Visit 10), Week 108 (Visit 11), Week 120 (Visit 12), Week 132 (Visit 13), Week 144 (Visit 14), Week 156 (Visit 15), Week 168 (Visit 16), Week 180 (Visit 17), Week 192 (Visit 18), Week 204 (Visit 19), Week 216 (Visit 20), Week 228 (Visit 21), Week 240 (Visit 22 End-of-Treatment/Premature Discontinuation) and at the Post-Treatment Visit (6 weeks post discontinuation of ataluren).

7.2.10. Hematology Laboratory Assessment

Hematology laboratory assessments will include white blood cell count with differential, hemoglobin, hematocrit, mean corpuscular volume, mean corpuscular hemoglobin, mean corpuscular hemoglobin concentration, total red cell count with morphology, and platelet count. These parameters will be measured at Screening (Visit 1), Week 1 (Visit 2), Week 12 (Visit 3), Week 24 (Visit 4), Week 36 (Visit 5), Week 48 (Visit 6), Week 60 (Visit 7), Week 72 (Visit 8), Week 84 (Visit 9), Week 96 (Visit 10), Week 108 (Visit 11), Week 120 (Visit 12), Week 132 (Visit 13), Week 144 (Visit 14), Week 156 (Visit 15), Week 168 (Visit 16), Week 180 (Visit 17), Week 192 (Visit 18), Week 204 (Visit 19), Week 216 (Visit 20), Week 228 (Visit 21), Week 240 (Visit 22 End-of-Treatment/Premature Discontinuation) and at the Post-Treatment Visit (6 weeks post discontinuation of ataluren). Hematology parameters will be analyzed by the central laboratory. The Covance Central Laboratory Manual should be consulted for collection, processing, and shipping details.

7.2.11. Serum Biochemistry Laboratory Assessment

Biochemistry laboratory assessments will include sodium, potassium, chloride, bicarbonate, blood urea nitrogen, creatinine, magnesium, calcium, phosphorus, uric acid, glucose, total protein, albumin, globulin, albumin:globulin ratio, bilirubin (direct and indirect), AST, ALT, GGT, CK, lactate dehydrogenase (LDH), alkaline phosphatase, total cholesterol, high-density lipoprotein (HDL), low-density lipoprotein (LDL), triglycerides, and cystatin C. These parameters will be measured at Screening (Visit 1), Week 1 (Visit 2), Week 12 (Visit 3), Week 24 (Visit 4), Week 36 (Visit 5), Week 48 (Visit 6), Week 60 (Visit 7), Week 72 (Visit 8), Week 84 (Visit 9), Week 96 (Visit 10), Week 108 (Visit 11), Week 120 (Visit 12), Week 132

(Visit 13), Week 144 (Visit 14), Week 156 (Visit 15), Week 168 (Visit 16), Week 180 (Visit 17), Week 192 (Visit 18), Week 204 (Visit 19), Week 216 (Visit 20), Week 228 (Visit 21), Week 240 (Visit 22 End-of-Treatment/Premature Discontinuation) and at the Post-Treatment Visit (6 weeks post discontinuation of ataluren). Subjects should have fasted for at least 8 hours prior to blood collection. Biochemistry parameters will be analyzed by the central laboratory. The Covance Central Laboratory Manual should be consulted for collection, processing, and shipping details.

7.2.12. Adrenal Laboratory Assessments

A plasma sample for ACTH and cortisol assessments will be collected. These parameters will be measured at Screening (Visit 1), Week 1 (Visit 2), Week 12 (Visit 3), Week 24 (Visit 4), Week 36 (Visit 5), Week 48 (Visit 6), Week 60 (Visit 7), Week 72 (Visit 8), Week 84 (Visit 9), Week 96 (Visit 10), Week 108 (Visit 11), Week 120 (Visit 12), Week 132 (Visit 13), Week 144 (Visit 14, Week 156 (Visit 15), Week 168 (Visit 16), Week 180 (Visit 17), Week 192 (Visit 18), Week 204 (Visit 19), Week 216 (Visit 20), Week 228 (Visit 21), Week 240 (Visit 22 End-of-Treatment/Premature Discontinuation) and at the Post-Treatment Visit (6 weeks post discontinuation of ataluren). These parameters will be analyzed by the central laboratory. The Central Laboratory Manual should be consulted for collection, processing, and shipping details.

Aldosterone and renin pre-treatment values will be measured at Screening (Visit 1), and, as necessary, for patients with treatment emergent evidence of adrenal dysfunction. These parameters will be analyzed by the central laboratory. The Covance Central Laboratory Manual should be consulted for collection, processing, and shipping details.

7.2.13. Urinalysis

Urinalysis will include analysis for pH, specific gravity, glucose, ketones, blood, protein, urobilinogen, bilirubin, nitrite, and leukocytes. These parameters will be measured at Screening (Visit 1), Week 1 (Visit 2), Week 12 (Visit 3), Week 24 (Visit 4), Week 36 (Visit 5), Week 48 (Visit 6), Week 60 (Visit 7), Week 72 (Visit 8), Week 84 (Visit 9), Week 96 (Visit 10), Week 108 (Visit 11), Week 120 (Visit 12), Week 132 (Visit 13), Week 144 (Visit 14), Week 156 (Visit 15), Week 168 (Visit 16), Week 180 (Visit 17), Week 192 (Visit 18), Week 204 (Visit 19), Week 216 (Visit 20), Week 228 (Visit 21), Week 240 (Visit 22 End-of-Treatment/Premature Discontinuation) and at the Post-Treatment Visit (6 weeks post discontinuation of ataluren). These parameters will be analyzed by the central laboratory. Urine samples will also be collected and shipped to central laboratory for assessment of urine protein, creatinine, osmolality and urinalysis. The Covance Central Laboratory Manual should be consulted for collection, processing, and shipping details.

7.2.14. 12-Lead ECG

A 12-lead ECG will be obtained at Screening (Visit 1) to establish a baseline tracing. Thereafter during the study, ECGs should be obtained as clinically indicated.

7.2.15. Echocardiogram

An echocardiogram will be obtained at Screening (Visit 1), Week 60 (Visit 7), Week 108 (Visit 11), Week 156 (Visit 15) and Week 216 (Visit 20). In addition, an echocardiogram will be

obtained at the Post-Treatment Visit (6 weeks post discontinuation of ataluren) in patients who discontinue the study after 240 weeks of treatment.

7.2.16. 6-Minute Walk Test

6MWD will be assessed in those patients who are ambulatory (able to run/walk 10 meters in ≤30 seconds) at study entry, using standardized procedures [McDonald 2010] (see Study Manual). The 6MWT will be performed at Screening (Visit 1), Week 24 (Visit 4), Week 48 (Visit 6), Week 72 (Visit 8), Week 96 (Visit 10), Week 120 (Visit 12), Week 144 (Visit 14), Week 168 (Visit 16), Week 192 (Visit 18), Week 216 (Visit 20) and Week 240 (Visit 22 End-of-Treatment/Premature Discontinuation).

7.2.17. Timed Function Tests

Timed function tests will performed in those patients who are ambulatory at study entry, and include the time taken to stand from supine and time taken to run/walk 10 meters [Mendell 1989, Griggs 1991, Beenakker 2005a, Pradhan 2006] (see Study Manual). These parameters will be monitored at Screening (Visit 1), Week 48 (Visit 6), Week 96 (Visit 10), Week 144 (Visit 14), Week 192 (Visit 18) and Week 240 (Visit 22 End-of-Treatment/Premature Discontinuation).

7.2.18. North Star Ambulatory Assessment

The NSAA will be used to evaluate physical function in those patients who are ambulatory at study entry, using standardized procedures (see Study Manual). The NSAA will be performed at Screening (Visit 1), Week 48 (Visit 6), Week 96 (Visit 10), Week 144 (Visit 14), Week 192 (Visit 18) and Week 240 (Visit 22 End-of-Treatment/Premature Discontinuation).

7.2.19. Egen Klassifikation Scale

Activities of daily living will be measured using the EK scale [Steffensen 2001] in nonambulatory patients (unable to run/walk 10 meters in ≤30 seconds). The EK scale will be completed at Screening (Visit 1), Week 48 (Visit 6), Week 96 (Visit 10), and Week 144 (Visit 14), Week 192 (Visit 18), and Week 240 (Visit 22 End-of-Treatment/Premature Discontinuation).

Please refer to the Study Manual for further details on how to administer the EK scale.

7.2.20. Spirometry

Spirometry will be conducted in nonambulatory patients. Spirometry will be performed at Screening (Visit 1), Week 24 (Visit 4), Week 48 (Visit 6), Week 72 (Visit 8), Week 96 (Visit 10), Week 120 (Visit 12), Week 144 (Visit 14), Week 168 (Visit 16), Week 192 (Visit 18), Week 216 (Visit 20) and Week 240 (Visit 22 End-of-Treatment/Premature Discontinuation).

7.2.21. Disease Status Survey

For all patients, a disease status survey will be administered at Screening (Visit 1) to collect retrospective information on patient and/or parent-reported changes in disease status during and after their participation in the prior PTC Therapeutics Studies 007 and 007e.

A separate survey will be administered at Week 1 (Visit 2), Week 12 (Visit 3), Week 24 (Visit 4), Week 36 (Visit 5), Week 48 (Visit 6), Week 60 (Visit 7), Week 72 (Visit 8), Week 84 (Visit 9), Week 96 (Visit 10), Week 108 (Visit 11), Week 120 (Visit 12), Week 132 (Visit 13), Week 144 (Visit 14), Week 156 (Visit 15), Week 168 (Visit 16), Week 180 (Visit 17), Week 192 (Visit 18), Week 204 (Visit 19), Week 216 (Visit 20), Week 228 (Visit 21), Week 240 (Visit 22 End-of-Treatment/Premature Discontinuation) to collect prospective information on patient and/or parent-reported changes in disease status.

7.2.22. Study Drug Administration

Subjects should take ataluren TID as described in Section 6.2.2. Ataluren supply sufficient for each 12-week treatment period will be supplied to the subject or caregiver, as appropriate. The patient is still required to be at the site for the 24-week (6-month) re-weigh visit. The amount of study drug supplied to the subject may be altered in the event of pending commercial availability or other reasons as noted in Section 6.2.1. Sufficient drug will be provided at each of these visits to lessen the likelihood that patients will experience drug shortages due to inadvertent loss of some of the sachets or scheduling delays for return visits.

Because of potential changes in subject body weight over time, an investigator site representative should enter the subject's current body weight into the IWR system at Week 24, Week 48, Week 72, Week 96, Week 120, Week 144, Week 168, Week 192 and Week 216 to obtain study drug dosing instructions. Depending upon the magnitude of change in subject body weight since baseline, the number and type of sachets to be used by the subject may remain the same or may be adjusted.

7.2.23. Study Drug Compliance

Ataluren compliance will be assessed using the electronic case report forms. The system will document the return of any unused drug sachets for compliance assessments.

Subjects or caregivers will return all unused sachets of ataluren to the investigator site for full compliance assessments.

7.2.24. Adverse Events

Adverse events must be assessed and documented at each clinic visit. This information will be collected at Week 1 (Visit 2), Week 12 (Visit 3), Week 24 (Visit 4), Week 36 (Visit 5), Week 48 (Visit 6), Week 60 (Visit 7), Week 72 (Visit 8), Week 84 (Visit 9), Week 96 (Visit 10), Week 108 (Visit 11), Week 120 (Visit 12), Week 132 (Visit 13), Week 144 (Visit 14), Week 156 (Visit 15), Week 168 (Visit 16), Week 180 (Visit 17), Week 192 (Visit 18), Week 204 (Visit 19), Week 216 (Visit 20), Week 228 (Visit 21), Week 240 (Visit 22 End-of-Treatment/Premature Discontinuation) and at the Post-Treatment Visit (6 weeks post discontinuation of ataluren). In

addition, patients/caregivers will be encouraged to report adverse events of concern at any time in the intervals between visits.

In addition, adverse events should be evaluated after the Post-Treatment Visit (6 weeks post discontinuation of ataluren) until any drug-related adverse events and/or ongoing SAEs have resolved or become stable, whichever occurs later.

7.2.25. Concomitant Medications

Information regarding any concomitant medications administered, as well as information regarding all non-drug therapies, will be collected throughout the study. This information will be collected at Screening (Visit 1), Week 1 (Visit 2), Week 12 (Visit 3), Week 24 (Visit 4), Week 36 (Visit 5), Week 48 (Visit 6), Week 60 (Visit 7), Week 72 (Visit 8), Week 84 (Visit 9), Week 96 (Visit 10), Week 108 (Visit 11), Week 120 (Visit 12), Week 132 (Visit 13), Week 144 (Visit 14), Week 156 (Visit 15), Week 168 (Visit 16), Week 180 (Visit 17), Week 192 (Visit 18), Week 204 (Visit 19), Week 216 (Visit 20), Week 228 (Visit 21), Week 240 (Visit 22 End-of-Treatment/Premature Discontinuation) and at the Post-Treatment Visit (6 weeks post discontinuation of ataluren).

7.3. Blood Collection Summary

Information regarding the types and approximate amounts of blood samples to be collected in the study is provided in Table 5. Assuming a 240-week treatment of ataluren, the approximate maximum amount of blood to be drawn at a visit is 22.5 mL and the total amount of blood to be drawn over the entire 240-week study period (including the Screening visit, the 240-week treatment period, and the 6-week follow-up period) is approximately 264.5 mL. Additional blood collection may be required in the event of an adverse events or laboratory abnormality.

Table 5 Blood Drawing Requirements

Test	Sample Type	Tube Type	Tube Top (Color)	Tube Size (mL)	Blood Per Tube (mL)	Number of Tubes		Total
Test						Per Visit	Total	Blood (mL)
Hematology	Whole blood	EDTA	Lavender	2	2	1	23	46
Hepatitis screen	Serum	Clot	Gold	3.5	3.5	1	1	3.5
Biochemistry	Serum	Clot	Gold	5	5	1	23	115
ACTH	Plasma	EDTA	Lavender	2	2	1	23	46
Cortisol	Plasma	EDTA	Lavender	2	2	1	23	46
Aldosterone and Renin	Plasma	EDTA	Lavender	8	8	1	1	8
Maximum Total								264.5

Abbreviations: ACTH = adrenocorticotropic hormone, EDTA = ethylenediaminetetraacetate

8. ADVERSE EVENT ASSESSMENTS

8.1. Adverse Event Definitions

8.1.1. Adverse Events

An adverse event is any untoward medical occurrence associated with the use of a drug (investigational medicinal product) in humans, whether or not it is considered related to the drug. An adverse event can therefore be any unfavorable and unintended sign (including an abnormal laboratory finding), symptom, or disease in a study subject who is administered ataluren in this study.

For this protocol, untoward medical occurrences that should be reported as adverse events include the following:

- All adverse events that are suspected to be due to ataluren.
- Overdose (administration of an ataluren dose >4 times the highest intended total daily dose level for this protocol [>160 mg/kg/day]) of ataluren.
- All reactions from medication misuse, abuse, withdrawal, sensitivity, or toxicity.
- All reactions that result from medication errors or uses of the study drug outside what is described in the protocol.
- Apparently unrelated illnesses, including the worsening of a preexisting illness.
- Injury or accidents. Note that if a medical condition is known to have caused the injury or accident (a fall secondary to dizziness), the medical condition (dizziness) and the accident (fall) should be reported as 2 separate adverse events. The outcome of the accident (hip fracture secondary to the fall) should be recorded in source documents.
- Abnormalities in physiological testing or physical examination findings that require clinical intervention or further investigation (beyond ordering a repeat [confirmatory] test).
- Laboratory or ECG abnormalities that require clinical intervention or further investigation (beyond ordering a repeat [confirmatory] test) unless they are associated with an already reported clinical event. Laboratory abnormalities associated with a clinical event (eg, elevated liver enzymes in a subject with jaundice) should be captured in the source documents. Laboratory abnormalities not requiring clinical intervention or further investigation will be captured as part of overall laboratory monitoring, and should not be reported as adverse events.
- A preexisting condition (eg, allergic rhinitis) must be noted on the appropriate electronic CRF (eCRF) for Visit 1, but should not be reported as an adverse event unless the condition worsens or episodes increase in frequency during the adverse event reporting period. Diagnostic and therapeutic non-invasive and invasive procedures, such as surgery, should not be reported as adverse events. However, the medical condition for which the procedure was performed should be reported if it meets the definition of an adverse event. For example, an acute appendicitis that begins during the adverse event reporting period should be reported as

the adverse event and the resulting appendectomy should be recorded in the source documents. If a surgical procedure was planned prior to entry into the study, and the surgery is not performed because of a worsening of a baseline condition, this should not be reported as an adverse event. Note that, as described in Section 8.1.2, any inpatient hospitalization occurring as the consequence of an adverse event during the study period should be reported as an SAE.

Each adverse event is to be classified as serious or nonserious by the investigator using medical and scientific judgment.

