3.3. Clinical Endpoints

Primary

• Safety profile characterized by type, frequency, severity, timing, and relationship to ataluren of any adverse events or laboratory abnormalities

Secondary

• In ambulatory patients, change from baseline in 6MWD as measured by the 6-minute walk test (6MWT)

- In ambulatory patients, change from baseline in physical function as measured by the North Star Ambulatory Assessment (NSAA)
- In ambulatory patients, change from baseline in timed function tests (time to stand from supine and time to run/walk 10 meters)
- In nonambulatory patients, change from baseline in pulmonary function as measured by spirometry
- In nonambulatory patients, change from baseline in patient and parent/caregiver-reported activities of daily living, as measured by the Egen Klassifikation (EK) scale
- In all patients, changes in patient and/or parent/caregiver reports of disease status as measured by a standardized survey administered by site personnel

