8.3. Adverse Event Recording

All adverse events (both serious and nonserious) that occur in patients during the adverse event reporting period must be recorded, whether or not the event is considered drug related. In addition, any known untoward event that occurs subsequent to the adverse event reporting period that the investigator assesses as possibly related to the investigational drug/product should also be recorded as an adverse event.

All adverse events are to be recorded in the source documents and on the CRF using concise medical terminology; whenever possible terms contained in Medical Dictionary for Regulatory Activities (MedDRA) should be employed. In addition, the following information should be recorded:

Indication of whether the event is serious or nonserious (see Section 8.1.2)

- Relationship to ataluren (see Section 8.4)
- Severity of the event (see Section 8.5)
- Onset date
- Resolution date, or date of death
- Action taken
- Outcome of the event

Classification of the event as serious or nonserious determines the reporting procedures to be followed.

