For SAEs, in addition to completing the adverse event portion of the CRF, the SAE report form must also be completed. The SAE report form should be signed by the investigator; however, if the investigator is unable to sign at the time of the event or within 24 hours, the form should be signed by the clinical staff member reporting the SAE (eg, the study coordinator). The SAE report form must be faxed or emailed to the PTC Therapeutics Safety Department and to the site IRB/IEC (if required by local regulations) within 24 hours. Follow up information to the SAE should be clearly documented as "follow up" in the SAE report form and must also be faxed or emailed to the same party. All follow up SAE report forms for the event must be signed by the investigator. Any source documents (eg, progress notes, nurses' notes, laboratory and diagnostic test results, discharge summaries) provided to the sponsor should be redacted so that the patient's name, address, and other personal identity information are obscured. Only the patient's study number and initials are to be provided. The information in the adverse event portion of the CRF and the SAE report form(s) must match or be reconciled. Where the same data are collected, the

forms must be completed in a consistent manner. For example, the same adverse event term should be used on both forms.

In the rare event that the investigator does not become aware of the occurrence of an SAE immediately (for example, if a subject initially seeks treatment elsewhere), the investigator is to report the event within 24 hours after learning of it and to document his/her first awareness of the adverse event.

The PTC Therapeutics Safety Department contact information for reporting serious adverse events is provided below. This information is also provided in the Study Manual and in the SAE report form.

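### Protocol section 8.1.1 makes a fall and its cause adverse events but sends the resulting injury to source documents, so injuries can be missing or unevenly captured in the adverse event tables

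*Protocol*

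**What the plan says.** The primary endpoint (Protocol section 3.3) is the "Safety profile characterized by type, frequency, severity, timing, and relationship to ataluren of any adverse events or laboratory abnormalities".

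Section 8.1.1 lists what sites must report. One bullet covers injuries and accidents. Its note says that where a medical condition is known to be the cause, "the medical condition (dizziness) and the accident (fall) should be reported as 2 separate adverse events". The next sentence deals with the consequence: "The outcome of the accident (hip fracture secondary to the fall) should be recorded in source documents".

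Section 8.3 sets the general rule: "All adverse events (both serious and nonserious) that occur in patients during the adverse event reporting period must be recorded", whether or not they are thought drug related. It also says where: "All adverse events are to be recorded in the source documents and on the CRF using concise medical terminology".

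For SAEs, section 8.9 requires the CRF and the SAE report form to agree; as its example, "the same adverse event term should be used on both forms".

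**The concern.** A hip fracture is an unwanted medical event in its own right and falls within section 8.1.1's own definition of an adverse event. Yet the worked example stops at two events and gives the fracture a different destination. A coordinator who follows it literally enters dizziness and fall on the CRF and writes the fracture in the chart.

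This matters because the study has no formal hypothesis (Protocol 10.1, SAP 3.4), so its adverse event tables are its main product. The population is also one in which falls are expected: Protocol section 2.1 describes boys who often fall by the age of 8, and the summary of Study 007 reports fall frequency as an outcome. Treatment is planned for 240 weeks, and the SAP allows visits to week 336 for the Canadian sites. Over that time, the type of injury that follows a fall is a substantive part of a long-term safety profile.

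**Working it through.** No arithmetic from the plan applies, so the check is to set the passages side by side and follow one event to the tables.

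**1. How section 8.1.1 uses source documents elsewhere.** Two other places give this destination.
- Laboratory changes tied to a clinical event: "Laboratory abnormalities associated with a clinical event (eg, elevated liver enzymes in a subject with jaundice) should be captured in the source documents". These come under an exception to the reporting rule.
- Procedures: an appendicitis is to be reported as "the adverse event and the resulting appendectomy should be recorded in the source documents". This follows a statement that procedures are not adverse events.

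In both, source documents replace a separate adverse event entry. A reader would naturally take the fracture sentence the same way. A fracture, however, is neither a procedure nor a laboratory finding that accompanies a reported diagnosis.

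**2. Text pointing the other way.**
- The bullet containing the note begins by naming injury as reportable.
- Another bullet makes physical examination findings reportable if they need clinical intervention or further investigation.
- The procedure rule says the condition that led to a procedure is reported if it meets the adverse event definition. A surgically repaired fracture is therefore reportable under that rule, while the hip fracture example sends it to source documents.
- Section 8.3 sends all adverse events to source documents and to the CRF.

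**3. One event, two defensible site practices.** Take a boy who becomes dizzy, falls and breaks a hip.

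| | Site following the 8.1.1 example | Site following the adverse event definition and 8.3 |
|---|---|---|
| Adverse events on CRF | dizziness, fall (2) | dizziness, fall, fracture (1 + 1 + 1 = 3) |
| Fracture preferred term | absent | present |
| Grade, onset and relationship of the fracture | not recorded separately | recorded separately |
| If admitted to hospital | SAE, likely under the fall | SAE, can be under the fracture |

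**4. From CRF to tables.** Protocol section 10.4.5.1 counts patients by MedDRA term. SAP section 5.7.1 tabulates treatment-emergent events by SOC and preferred term, with further tables for serious, Grade 3 or higher, treatment-related and common (5% or more) events, and an exposure-adjusted rate based on event counts. SAP section 5.1 builds listings from CRF modules. Neither document plans a fracture analysis or another route from source documents into these tables. Section 8.3 does record an outcome for each event, but no plan codes or tabulates that field by preferred term. The difference in the table above therefore passes straight into the results.

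**5. Size.** The number of affected patients depends on the fracture rate after accidents and on how many sites followed the example. The documents give neither figure.

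**The case against.** The strongest reply is that the sentence does not say the injury goes only to source documents, nor that it must not be reported. Where section 8.1.1 means to exclude something, it says so, as it does for minor laboratory changes and for procedures. Reporting two separate events does not forbid a third. On this reading section 8.3 governs, and source recording is simply the first step of the normal route. This stands in part: exclusivity is an inference from the contrast within the example and from the section's other uses of the phrase. It does not remove the problem, because the one worked example names a fracture and omits the CRF.

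A reader might go further and infer that fractures drop out of the primary endpoint, or that the drafters meant to keep them out. The documents support neither. The note opens with accidents caused by a medical condition, and a fracture without an accident is untouched. The fall remains on the CRF and can carry a grade and an outcome. An admission resulting from an adverse event is an SAE under section 8.1.1. Nothing in the text shows intent.

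It is also fair that serious cases reach the sponsor: Table 8 sends source records to the safety department within 5 calendar days, and the same-term rule allows fracture to be entered on both forms. Non-drug therapies are collected, coded and summarised under SAP section 5.5. These routes may bring an injury to the sponsor's notice, but they do not by themselves place it in the adverse event tables. The Study Manual and any CRF completion instructions might give clearer guidance, but they are not among the documents.

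**Conclusion.** The concern holds as an internal contradiction with a consequence for the primary endpoint. The example in section 8.1.1 conflicts with the opening of its own bullet, with the procedure rule in the same section and with section 8.3. As written, it permits the same injury to be coded at one site and left out at another. The patient, the fall and any resulting SAE remain counted. What is at risk is the injury as its own event, with its own preferred term, grade, onset and relationship, in the SOC and preferred term, serious, Grade 3 or higher and treatment-related tables.

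No number of affected boys can be stated. Any such figure would rest on an assumed fracture rate that the documents do not supply. The conclusion assumes only that some sites follow the example as written and that no site instruction outside these documents overrides it. It should be fixed, because the remedy is cheap and the affected tables are the primary analysis; it does not invalidate the study.

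**What to change.** Replace the sentence in section 8.1.1 with one stating that an injury resulting from an accident (for example a fracture or head injury) is reported on the adverse event CRF as a separate adverse event, with its own onset date, severity, seriousness and relationship. Align any CRF completion instructions, so that the bullet, the procedure rule and section 8.3 say the same thing.

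SAP section 5.2 says the sponsor has decided to discontinue the study, so a change of wording alone will alter little of the data. The more useful step is retrospective: before database lock, list all reported falls and other accidents, query sites for resulting injuries against source documents and SAE reports, and add those found to the CRF. The documents do not say whether lock has occurred. If it has, a note beside the adverse event tables should say that injuries following accidents may appear only under the accident term and that capture may differ between sites.

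The cost is one sentence, one query listing with site follow-up, and probably a slightly higher adverse event count.
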